Phase II (recovery): Moreover, we also propose to examine the effectiveness of daily use of electrical stimulation therapy to recover from the long-term neuromuscular side effects of prolonged immobilization in patients who were bedbound due to COVID-19. These effects include lower extremity critical illness myopathy and neuropathy. Lengthened periods of immobilization decreases muscle activity provoking atrophy, weakness, and pain. We hypothesize that electrical stimulation will help to increase muscle fiber activation and nerve conductivity, thus, help in recovery of the neuromuscular condition.

Section E: Protocol Risks/Subjects

E1. Risk Category

Category 1: Research not involving greater than minimum risk.

E2. Subjects

Gender:

Both

Age:

Adult (18-64 yrs), Geriatric (65+ yrs)

Ethnicity:

All Ethnicities

Primary Language: English

Groups to be recruited will include: Patients

Which if any of the following vulnerable populations will be recruited as subjects?

Cognitively impaired

Vulnerable populations require special protections. How will you obtain informed consent, protect subject confidentiality, and prevent undue coercion?

Due to no visitation, the consent will be done over the phone by the physician with a legal representative of the patient. Two nurses will be present during the call and the consenting will be done by the physician following current consenting procedures with other ongoing studies in the hospital. This study has minimal risks for the patient, all notes will be added to the consent form based on the call. If patient is able to give verbal consent will be singed physically.

For patients who lack the capacity to consent, the investigator/designee may explain the study to the legally authorized representative by phone. The discussion will be documented in the subject's medical record or research chart. Two copies of the unsigned consent form will be sent to the subject/legal representative with instructions for completion of the signature page and assent (if applicable). Signatures will be obtained according to standard Baylor IRB regulations. The subject will be told to keep one form and returned the other to the investigator by mail, email, or fax. The Baylor Investigator/designee will sign the consent form when returned from the subject. The signed consent form will be maintained in research records.

E3. Pregnant woman/fetus

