Will pregnant women and/or fetuses (as described in 45 CFR 46 Subpart B) be enrolled in the research? No

E4. Neonates

Will neonates of uncertain viability or nonviable neonates (as described in 45 CFR 46 Subpart B) be enrolled in the research? No

E5. Children

Will children be enrolled in the research? No

Section F: Design/Procedure

F1. Design

Select one category that most adequately describes your research: c) Pilot

Discuss the research design including but not limited to such issues as: probability of group assignment, potential for subject to be randomized to placebo group, use of control subjects, etc.

Phase I: 20 subjects with COVID-19 infection that are being treated in the hospital. This means that this patient population is positive to COVID-19 and have been admitted with no more than 48 hours to the hospital due to severe infection. In some cases, the patients will not able to consent at the time of enrollment. This determines a high grade of severity of illness. Therefore, a family member/legal representative will be contacted via telephone for consenting. Participants will be randomized to intervention (IG) or control group (CG). The entire cohort will receive daily EE in lower extremity (e.g. Gastronemius, tibial anterior muscle) up to 1 hour. EE therapy will be provided using portable device. The EE device will be functional for IG and non-functional for CG. The duration of the study will be 2 weeks or until patient discharge, whichever comes first. The primary outcomes include between group difference and change from the baseline in muscle endurance, muscle strength, lower extremity tissue oxygen saturation, neuropathy, and muscle atrophy. Outcomes will be assessed at baseline, time of discharge or 2 weeks, whichever comes first. Due to the condition of the patient we are looking to reduce the interaction with staff, the device will be placed with no additional requirements. Physical therapy targets other physical performances, this device is aimed to improve blood flow, tissue perfusion and muscle activation while the patient is non-responsive to physical activities.

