Physical Activity Monitoring: The subject will be given a wearable device (PAMSys) or a smart watch, that will be measuring several parameters including number of steps taken, duration of sitting, standing, walking and lying, time taken and number of transitions from sit to stand, and walking speed for 48 hours. At the end of the specific visit, the subject will be given the device, if they are given PAMSys it will be attached to pendant to wear around the neck, otherwise they may wear the smart watch on their wrist. Investigators will provide a pre-paid envelope where the subject may place the device and send back it to the investigating team.

Oxygen Level Assessment: Oxygen saturation will be measured using a pulse oximeter.

The supervision of this study will be by pulmonary care specialists, and the location will be at Baylor College of Medicine McNair Campus.

Section G: Sample Size/Data Analysis

G1. Sample Size

How many subjects (or specimens, or charts) will be used in this study? Local: 40 Worldwide: 40

Please indicate why you chose the sample size proposed:

Sample size is convenient and selected based on available resources to demonstrate feasibility and the proof of concept effectiveness of EE therapy for COVID-19 patients admitted to ICU and post-ICU. We plan to recruit 40 eligible subjects.

G2. Data Analysis

Provide a description of your plan for data analysis. State the types of comparisons you plan (e.g. comparison of means, comparison of proportions, regressions, analysis of variance). Which is the PRIMARY comparison/analysis? How will the analyses proposed relate to the primary purposes of your study?

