P-values of 0.05 or less will be considered statistically significant based on a two-sided test unless otherwise noted. All variables will be tabulated descriptively at each scheduled time point (baseline and discharge date). For each continuous variable, the analyses will include the mean, standard deviation, minimum and maximum. For each categorical variable, the summary will include frequencies and percentages. Each variable will be analyzed using all available data. Baseline variables will be summarized using descriptive statistics. We assume that a successful intervention is also helpful to maintain subjects muscle mass, reduce neuromyopathy signs and increase venous return flow. The measured parameters (e.g. muscle circumference, sEMG, kent imaging, doppler, etc.) should change substantially from baseline to the end of the intervention. For example, the EMG amplitude values should show increased voltages. Next, for all continuous variables, pre-treatment scores will be regressed on post-treatment scores to form residualized change scores (e.g. sEMG, VPT, dynamometer, etc). Correlations will then be generated among these scores to determine whether changes in sEMG factors are related appropriately with increases in (clinically assessed) functional capacities and self-report measures of activities. ANOVA test will be used to examine significant difference between patients with severe risk factors for prolonged ICU stage (e.g. age, BMI, cardiovascular morbidities). Moderator effects will also be examined for exploratory purposes. Using gender as an example, mixed design ANOVAs will be conducted to determine whether mobility factors change over the course of treatment at different rates or with different patterns for men and women. Additional analyses will test whether changes in muscle strenght and neuropathy (e.g. VPT and dynamometer assessement at time of discharge).

Section H: Potential Risks/Discomforts

H1. Potential Risks/Discomforts

Describe and assess any potential risks/discomforts; (physical, psychological, social, legal, or other) and assess the likelihood and seriousness of such risks:

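### G2 correlates sEMG change with functional change without an arm term or a rule for the two phases, so a device effect on both measures can produce or inflate the correlation

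*Combined protocol and SAP*

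**What the plan says.** Section G2 builds the analysis in two steps. For all continuous variables, "pre-treatment scores will be regressed on post-treatment scores to form residualized change scores". Then: "Correlations will then be generated among these scores to determine whether changes in sEMG factors are related appropriately" with gains in clinically assessed functional capacity and in self-reported activity. Neither step mentions randomized arm or study phase. The general rules around them are "Each variable will be analyzed using all available data" and "P-values of 0.05 or less will be considered statistically significant based on a two-sided test unless otherwise noted". The only scheduled time points G2 names are baseline and discharge.

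Section F1 randomizes both phases to a functional or a non-functional device, with 20 patients in each phase. F2 gives 10 per arm for Phase II; no split is stated for Phase I. G1 gives the total: "We plan to recruit 40 eligible subjects".

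The plan expects the device to act on these measures. Section D says of Phase II that "electrical stimulation will help to increase muscle fiber activation and nerve conductivity", and G2 expects EMG amplitudes to rise. F1 lists muscle strength among the outcomes to be compared between arms.

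The mixed models and GEEs that test the intervention effect are described in Section I, one outcome at a time. They do not cover the correlations.

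**The concern.** The question G2 asks is about patients: does someone whose sEMG improves also gain function? A correlation taken across both arms mixes that question with another one, whether the device shifted both averages. If it did, active patients tend to sit high on both scores and controls low on both. A correlation then appears even if, within each arm, sEMG change says nothing about functional change. The better the device works, the larger this component.

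A second, conditional problem concerns phase. Section D expects muscle loss during the Phase I hospital stay and recovery in Phase II. If the phases were combined, a difference in their average course would act on the correlation in the same way as a difference between arms.

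At stake is the interpretation of the correlation. Section I hopes the study will help in designing a practical method for assessing neuromyopathy, so these correlations could influence which measures are carried forward.

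**Working it through.** The plan states no effect size, SD, target correlation or power for this analysis, so there is no figure to reproduce. What can be checked is the mechanism and its size under stated assumptions.

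**Inputs from the documents.** Two-sided 0.05 (G2); 20 patients per phase (F1); 10 per arm in Phase II (F2).

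**Assumptions.** 10 per arm in Phase I; correlation of zero between the two measures inside each arm; pre-post correlation 0.6 for each measure; an equal arm shift d on both measures, in SDs of the post score given the pre score. With pre-post correlation 0.6 that SD is √(1−0.36) = 0.8 of the raw SD, so d = 1 means 0.8 raw SD.

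**Formula.** For two equal groups that differ by d on both scores, with no within-group relation, r = (d²/4)/(1 + d²/4).

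- d = 0.8: 0.16/1.16 = 0.138
- d = 1: 0.25/1.25 = 0.20
- d = 1.5: 0.5625/1.5625 = 0.36
- d = 2: 1/2 = 0.50

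If the device moves only one of the two measures, the numerator is zero and so is the induced correlation.

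**Simulation, one phase, n=20** (4,000 trials per row; critical r = 0.444):

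| Arm shift d | Mean r, post on pre | p<0.05 | p<0.05 with arm in model | Mean r, pre on post (as worded) | p<0.05 (as worded) |
|---|---|---|---|---|---|
| 0 | 0.00 | 5% | 5% | 0.00 | 5% |
| 0.5 | 0.05 | 5% | 4% | 0.02 | 5% |
| 0.8 | 0.14 | 9% | 5% | 0.04 | 6% |
| 1 | 0.20 | 13% | 4% | 0.06 | 6% |
| 1.5 | 0.35 | 34% | 4% | 0.10 | 7% |
| 2 | 0.49 | 63% | 4% | 0.11 | 7% |

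Simulation error at 34% is √(0.343×0.657/4000) = 0.0075, so 33% and 34% are the same result. With arm in the model the mean correlation is about 0.00 in every row.

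**Why the literal wording gives less.** Take d = 1. The post score shifts by 0.8 and its variance across arms is 1 + 0.8²/4 = 1.16. The slope of pre on post is 0.6/1.16 = 0.517, so the residual differs between arms by 0.517×0.8 = 0.414. Its within-arm variance is 1 − 2(0.517)(0.6) + 0.517² = 0.647, SD 0.804. The effective shift is 0.414/0.804 = 0.515, and r = (0.515²/4)/(1 + 0.515²/4) = 0.062, as simulated.

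**If the phases were pooled, n=40** (critical r = 0.312; post on pre; no arm effect). Phase gaps of 0.5, 1, 1.5 and 2 SD on both measures give r of 0.06, 0.20, 0.36 and 0.49, significant in 7%, 23%, 65% and 94% of trials. With arm and phase in the model this returns to about 5%. With scores formed as worded, the 2 SD gap gives r = 0.11 and 10%.

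**The case against.** Several objections have force.

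A reader might infer that the correlations are run over all 40 patients. The documents do not say so. The 40 in G1 answers a form question about headcount. The phases have separate randomizations, populations and schedules, and the time points in G2 fit Phase I. The plan is silent on pooling, and silence is all that can be claimed. Nor could pooling affect every correlation: questionnaires are listed only for Phase II visits, so phase bias could reach only measures taken in both phases, such as sEMG, VPT, dynamometer and circumference. The near-certain false correlation at n=40 also needs an assumed 2 SD gap between phases on both measures, which nothing in the documents supports. The 10% loss cited in Section D is muscle mass, not sEMG.

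A reader might also infer that the arm effect alone creates the correlation. At shifts of 0.5 to 0.8 SD, significance is 5% to 9%, close to nominal. That it can produce or inflate the correlation is as far as the figures go.

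The regression direction matters too. With scores formed exactly as G2 words them, the induced correlation is at most about 0.11 at a pre-post correlation of 0.6, though it grows when pre and post are more strongly correlated. That reduces the concern but does not remove it. Pre on post is not the usual residualized change score, and if the usual form is what is meant, the larger figures apply.

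It can be argued that shared movement caused by the device is itself part of whether sEMG and function go together. That is a fair choice of estimand, and a reason to show both correlations. It does not justify leaving arm unmentioned.

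Finally, no passage calls sEMG a surrogate or says that these correlations will validate one, so a claim of that harm would be speculative.

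**Conclusion.** The point holds in a limited form. G2 specifies no arm term for the sEMG-function correlations, no other section supplies one, and the handling of phase is unstated. Within a single phase of 20, an arm effect on both measures of 1 SD or more gives a noticeable false-positive rate with post-on-pre scores, rising from 13% at 1 SD to 63% at 2 SD. Below that the excess is small. These figures rest on assumed equal shifts on both measures, no within-arm relation, a pre-post correlation of 0.6 and equal arms.

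The arm problem does not depend on whether phases are pooled. The phase problem arises only if they are, and only for shared measures.

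This is a supporting, exploratory-type analysis in a convenience-sized pilot. The tests of the intervention effect described in Section I are not affected. It is worth correcting because the correction is nearly free.

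**What to change.** Amend G2 to say that:

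- residualized change scores are formed by regressing the post-treatment value on the pre-treatment value;
- the correlations are computed separately within Phase I and Phase II, as partial correlations given randomized arm, each with a 95% confidence interval;
- the post-treatment time point is named for each phase, since G2 now names only discharge;
- the unadjusted correlation may be shown alongside, labelled as including the device effect.

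The intervals matter at this size. With 20 patients and one adjustment variable, the Fisher z standard error is about 1/√(20−3−1) = 0.25. An observed correlation of zero then has an interval of about ±tanh(1.96×0.25) = ±0.45.

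The cost is a few lines of text and one degree of freedom per correlation. No new data are needed.

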activation. The device is used to reduce pain. However, the proposed treatment may assist in preventing or improving hospital-acquired Weakness because of prolonged hospital stay . In addition, the participation in this study may help the investigators better understand how COVID19 may impact cause myopathy and neuropathy and how to best help these patients to recover from prolonged hospital-stay .

Primary outcomes include neuropathy (assessed using VPT test); muscle function (assessed using sEMG), and tissue oxygenation (assessed using Kent Imaging). Secondary outcomes include weakness (assessed using dynamometer); muscle atrophy (assessed by weight loss as well as measuring ankle, calf, and thigh circumference); venous return flow (Doppler US [optional]); frailty (frailtymeter [optiona]); hospital length of stay (patient medical record); and major adverse events (patient health record). The primary and secondary outcomes will be assessed at baseline (if feasible) and on biweekly basis up to 4 weeks or hospital discharge, whichever came first. Appropriate mixed models (linear for continuous or Generalized Estimating Equations (GEEs) for non-continuous or non-parametric variables) will be used to test the intervention effect for each of the primary (e.g., tissue perfusion, tissue oxygen delivery, neuropathy severity, and myopathy incident) or secondary (e.g., frailty, weight loss, MAE, etc) outcomes.

Also, participation may help the investigators design a practical assessing method to identify the impact of neuromyopathy in the hospital setting. This may allow physicians to provide personalized care by monitoring muscle loss and limb complications caused by prolonged hospital length of stay.

Describe potential benefit(s) to society of the planned work.

As described above, this type of work may allow physicians to provide more personalized care for hospitalized patients in need of physical therapy for continuous and prolonged periods, specially when having a severe illness that includes medical staff risk contact.

Do anticipated benefits outweigh potential risks? Discuss the risk-to-benefit ratio.

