Patients enrolled will be alert and aware, there will not be patients with loss of consciousness enrolled in this phase. Optional assessments or surveys are not primary outcomes and so this information will not be collected from previously enrolled subjects. Pl/research staff will review the study and ICF with subject, asking questions to gauge comprehension. Control group subjects who already completed the study will be called to assess willingness to participate for 4 more weeks with an active device. If they agree, they will be reconsented in-person at the next visit or an email copy will be sent to sign and return via email. Completed active group subjects will be called and reconsented. The consent form will be sent via email and we will request that they email the signed copy back. Signed ICF will be kept in research records and a copy will be sent to all subjects via email.

Are foreign language consent forms required for this protocol?

No

J3. Privacy and Intrusiveness

Will the research involve observation or intrusion in situations where the subjects would normally have an expectation of privacy?

No

J4. Children

Will children be enrolled in the research?

No

J5. Neonates

Will non-viable neonates or neonates of uncertain viability be involved in research? No

J6. Consent Capacity - Adults who lack capacity

Will Adult subjects who lack the capacity to give informed consent be enrolled in the research? Yes

J7. Prisoners

Will Prisoners be enrolled in the research? No

Section K: Research Related Health Information and Confidentiality

Will research data include identifiable subject information? Yes

Information from health records such as diagnoses, progress notes, medications, lab or radiology findings, etc. Yes

Specific information concerning alcohol abuse:

Yes

Specific information concerning drug abuse: Yes

Specific information concerning sickle cell anemia: No

Specific information concerning HIV:

No

Specific information concerning psychiatry notes: No

Demographic information (name, D.O.B., age, gender, race, etc.): Yes

Full Social Security #: No

Partial Social Security # (Last four digits): No

Billing or financial records:

Yes

Photographs, videotapes, and/or audiotapes of you: Yes

Identifiable biospecimens

No

Other:

No

At what institution will the physical research data be kept? The physical research will be kept in our BCM offices housed in the Mcnair Building room B10.401.

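### G2's ANOVAs need age and BMI cut into undefined groups and conventionally use only complete patients; continuous terms and a mixed model would serve both questions better

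*Combined protocol and SAP*

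**What the plan says.** Section G2 (Data Analysis) plans two separate ANOVA analyses.

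- **Risk factors.** "ANOVA test will be used to examine significant difference between patients with severe risk factors for prolonged ICU stage (e.g. age, BMI, cardiovascular morbidities"). G2 gives no groups or cut-points for age or BMI, no definition of severe, and no outcome for this test.
- **Moderators.** "Moderator effects will also be examined for exploratory purposes". With gender as the example, "mixed design ANOVAs will be conducted to determine whether mobility factors change over the course of treatment", at different rates or in different patterns for men and women.

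Two general statements in G2 bear on both. One is "P-values of 0.05 or less will be considered statistically significant based on a two-sided test unless otherwise noted". The other is "Each variable will be analyzed using all available data", which stands among the sentences on descriptive summaries.

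A mixed model appears only in Section I (Potential Benefits): "Appropriate mixed models (linear for continuous or Generalized Estimating Equations (GEEs) for non-continuous or non-parametric variables) will be used to test the intervention effect" on the primary and secondary outcomes. G2 does not mention it, and Section I does not assign it to risk factors or moderators.

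The number of time points depends on where one looks. G2 names baseline and discharge. Section I has two-weekly assessment up to 4 weeks or discharge. Section F2 gives Phase II five visits, weeks 0 to 4. Gait, balance and activity measures are optional in F2. Section J2 says of optional assessments that "this information will not be collected from previously enrolled subjects".

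**The concern.** Age and BMI are continuous. Comparing patients by ANOVA on them means grouping them, which discards information and leaves the cut-points to be chosen after the data are seen. Each phase has 20 patients, so there is little information to spare.

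The mixed-design ANOVA raises a different problem. In its usual form it needs a reading from every patient at every time point, and patients with a gap leave the analysis. Mobility is where gaps are most likely, because the measures are optional, F2 expects that some patients cannot do the gait and balance tests, and earlier enrollees are not measured. The moderator result could then rest on a small and selected subset, although G2 says that all available data will be used.

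**Working it through.** **No figure of the plan to reproduce.** G1 calls the sample one of convenience and gives no power, effect size, standard deviation or dropout rate. Only the total can be checked: 20 + 20 = 40, as stated. Everything below except the sample sizes, visit counts and the two-sided 0.05 level is assumed.

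**1. Cost of grouping age or BMI.** Assume a normal covariate, a median split and a two-sided 0.05 test (20,000 simulated samples per row).

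| n | True correlation | Power, continuous | Power, median split |
|---|---|---|---|
| 20 | 0.3 | 0.26 | 0.17 |
| 20 | 0.4 | 0.43 | 0.28 |
| 20 | 0.5 | 0.64 | 0.42 |
| 20 | 0.6 | 0.84 | 0.60 |
| 40 | 0.3 | 0.48 | 0.32 |
| 40 | 0.4 | 0.74 | 0.53 |
| 40 | 0.5 | 0.92 | 0.76 |
| 40 | 0.6 | 0.99 | 0.91 |

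A hand check agrees. A median split of a normal variable keeps 2/π ≈ 0.64 of the information and so multiplies the correlation by √0.64 ≈ 0.80. A correlation of 0.5 then acts like 0.5 × 0.80 = 0.40. At n = 20 the continuous power at 0.4 is 0.43, close to the simulated 0.42.

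Both sample sizes are shown because G2 does not say whether this ANOVA is run within a phase or across both.

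**2. Cost of free cut-points.** With no true association and n = 20, taking the best of three cuts (near one third, one half and two thirds) gives about 11% false positives instead of 5%. The best of eleven cuts gives about 21%.

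**3. Cost of requiring complete readings.** Assume that baseline is always observed, that every visit is meant to have a mobility reading, and that a share m is missing independently at each of k follow-ups. Complete patients = 20 × (1 − m)^k. Share of planned readings that a mixed model uses = [1 + k(1 − m)] / (k + 1).

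| Schedule | k | m | Complete patients of 20 | Readings used by mixed model |
|---|---|---|---|---|
| G2: baseline and discharge | 1 | 10% | 20 × 0.9 = 18 | 95% |
| | 1 | 20% | 20 × 0.8 = 16 | 90% |
| Section I: two-weekly to 4 weeks | 2 | 10% | 20 × 0.81 = 16.2 | 93% |
| | 2 | 20% | 20 × 0.64 = 12.8 | 87% |
| F2, Phase II: five visits | 4 | 10% | 20 × 0.656 = 13.1 | 92% |
| | 4 | 20% | 20 × 0.410 = 8.2 | 84% |

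**4. What this does to power.** A small simulation (300 runs; n = 20, within-patient correlation 0.6, group-by-time effect of 1 SD, data missing completely at random) compared complete-case analysis with a random-intercept mixed model. Over five visits, power was about 0.50 against 0.74 at 10% missing, and 0.30 against 0.71 at 20%. With two time points it was 0.61 against 0.60, and 0.55 against 0.58, which is no real difference. With 300 runs the standard error is up to √(0.5 × 0.5 / 300) ≈ 0.03, so only the pattern should be read from these figures.

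**The case against.** The strongest objection is that the plan nowhere says that patients with a missed visit are dropped. A reader might infer that it does, but deletion is the usual behaviour of the method, not a rule in the documents, and G2's one sentence on the matter points the other way. This stands: what can be said is that the method and the all-available-data statement are unreconciled. It is also open whether that statement governs the models or only the summaries.

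Other limits also stand.

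- The deletion issue belongs to the moderator analysis, whose example, gender, needs no cut-point. The grouping issue belongs to the risk-factor ANOVA.
- The figures of 13 or 8 of 20 apply only to the Phase II schedule.
- The loss of about a third of the information assumes a median split of a normal covariate, which G2 does not specify. It cannot apply to cardiovascular morbidity if that is recorded as yes/no.
- It is tempting to say that the plan already holds a model that would use all the data. Section I gives its model to the intervention effect, so the moderator terms have to be added. No mixed model recovers earlier enrollees who have no mobility readings.
- This is a pilot, the moderator analyses are labelled exploratory, and neither ANOVA is the treatment comparison.

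The last point limits the weight of the finding but does not remove it. The exploratory label is attached to the moderator effects. The risk-factor ANOVA carries no such label and falls under the general 0.05 rule.

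**Conclusion.** The point holds in two limited parts. First, the ANOVA on age and BMI needs groups that G2 does not define. If a median split of a normal covariate were used, power at a true correlation of 0.5 would fall by about 22 percentage points at n = 20 (64% to 42%) and 16 at n = 40 (92% to 76%). This part does not depend on missing data.

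Second, the mixed-design ANOVAs conventionally need complete readings, which conflicts with G2's all-available-data statement. The cost is material for five Phase II visits, with about 13 or 8 of 20 patients complete at an assumed 10% or 20% missing per follow-up visit. It is minor for baseline and discharge only, with 18 or 16 of 20 complete. Missingness was taken as independent between visits. Gaps that follow severity or the date of enrolment would behave differently.

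The documents do not support the stronger readings that patients will be dropped or that the Section I model as written already solves this. The treatment comparison is not affected. The change is worth making because a better analysis is available at almost no cost.

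**What to change.** In G2:

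1. Enter age and BMI as continuous terms and cardiovascular morbidity as yes/no, and name the outcome. If groups are wanted for display, fix the cut-points now.
2. Replace the mixed-design ANOVAs with a linear mixed model of the kind named in Section I, brought into G2. Include arm, visit, the moderator (for example gender) and the moderator-by-visit interaction, which is the term that answers G2's question about different rates or patterns. Fit one moderator at a time, given the small sample.
3. State that the model uses every observed reading under a missing-at-random assumption. Add that patients with no mobility readings, such as earlier enrollees, are not recovered, and report how many there are.
4. Label both the risk-factor and the moderator analyses exploratory.

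The cost is wording in G2 and slightly more modelling work, with no new data or visits. The analysis then relies on a linear form for age and BMI and on missing at random. The second may fail where gaps follow severity of illness, so the report should say so.
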